10.2. Evaluation of Adverse Events

A qualified Investigator will evaluate all adverse events as to:

10.2.1. Seriousness

A serious adverse event (SAE) is any AE occurring at any dose that:

- Results in death;
- Is life-threatening (ie, in the opinion of the Investigator, the subject is at immediate risk of death from the AE);
- Requires inpatient hospitalization or prolongation of existing hospitalization (hospitalization is defined as an inpatient admission, regardless of length of stay);
- Results in persistent or significant disability/incapacity (a substantial disruption of the subject's ability to conduct normal life functions);
- Is a congenital anomaly/birth defect;

- Constitutes an important medical event.

Important medical events are defined as those occurrences that may not be immediately life threatening or result in death, hospitalization, or disability, but may jeopardize the subject or require medical or surgical intervention to prevent one of the other outcomes listed above. Medical and scientific judgment should be exercised in deciding whether such an AE should be considered serious.

Events **not considered** to be SAEs are hospitalizations for:

- A standard procedure for protocol therapy administration. However, hospitalization or prolonged hospitalization for a complication of therapy administration will be reported as an SAE.
- Routine treatment or monitoring of the studied indication not associated with any deterioration in condition.
- The administration of blood or platelet transfusion as routine treatment of studied indication. However, hospitalization or prolonged hospitalization for a complication of such transfusion remains a reportable SAE.
- A procedure for protocol/disease-related investigations (eg, surgery, scans, endoscopy, sampling for laboratory tests, bone marrow sampling). However, hospitalization or prolonged hospitalization for a complication of such procedures remains a reportable SAE.
- Hospitalization or prolongation of hospitalization for technical, practical, or social reasons, in absence of an AE.
- A procedure that is planned (ie, planned prior to starting of treatment on study); must be documented in the source document and the eCRF. Hospitalization or prolonged hospitalization for a complication remains a reportable SAE.
- An elective treatment of or an elective procedure for a pre-existing condition unrelated to the studied indication.
- Emergency outpatient treatment or observation that does not result in admission, unless fulfilling other seriousness criteria above.

If an AE is considered serious, both the AE page/screen of the eCRF and the SAE Report Form must be completed.

For each SAE, the Investigator will provide information on severity, start and stop dates, relationship to investigational product, action taken regarding investigational product, and outcome.

10.2.2. Severity / Intensity

For both AEs and SAEs, the Investigator must assess the severity/intensity of the event.

The severity of AEs will be graded based upon the subject's symptoms according to CTCAE version 5.0 with unique clinical descriptions of severity for each AE based on this general guideline:

- Grade 1 = Mild –asymptomatic or mild symptoms; clinical or diagnostic observations only; intervention not indicated
- Grade 2 = Moderate – minimal, local or noninvasive intervention indicated; limiting age-appropriate instrumental activities of daily living (ADL)
- Grade 3 = Severe or medically significant but not immediately life-threatening; hospitalization or prolongation of hospitalization indicated; disabling; limiting self-care ADL
- Grade 4 = Life-threatening consequences; urgent intervention indicated.
- Grade 5 = Death related to AE.

The term “severe” is often used to describe the intensity of a specific event (as in mild, moderate or severe myocardial infarction); the event itself, however, may be of relatively minor medical significance (such as severe headache). This criterion is *not* the same as “serious” which is based on subject/event *outcome* or *action* criteria associated with events that pose a threat to a subject’s life or functioning.

Seriousness, not severity, serves as a guide for defining regulatory obligations.

10.2.3. Causality

An Investigator who is qualified in medicine must make the determination of relationship to the investigational product for each AE (Unrelated, Possibly Related or Probably Related). The Investigator should decide whether, in his or her medical judgment, there is a reasonable possibility that the event may have been caused by the investigational product. If no valid reason exists for suggesting a relationship, then the AE should be classified as “unrelated.” If there is any valid reason, even if undetermined, for suspecting a possible cause-and-effect relationship between the investigational product and the occurrence of the AE, then the AE should be considered “related.”

If the relationship between the AE/SAE and the investigational product is determined to be “possible” or “probable” the event will be considered to be related to the investigational product for the purposes of expedited regulatory reporting.

10.2.4. Duration

For both AEs and SAEs, the Investigator will provide a record of the start and stop dates of the event.

10.2.5. Action Taken

The Investigator will report the action taken with investigational product as a result of an AE or SAE, as applicable (e.g., discontinuation, interruption, or reduction of study treatment, as appropriate) and report if concomitant and/or additional treatments were given for the event.

10.2.6. Outcome

All SAEs that have not resolved upon discontinuation of the subject's participation in the study must be followed until recovered, recovered with sequelae, not recovered or death (due to the SAE).

10.3. Abnormal Laboratory Values

An abnormal laboratory value is considered to be an AE if the abnormality:

- results in discontinuation from the study; or
- requires treatment, modification/ interruption of study treatment dose, or any other therapeutic intervention; or
- is judged to be of significant clinical importance

Regardless of severity grade (per CTCAE version 5.0), only laboratory abnormalities that fulfill a seriousness criterion need to be documented as a serious adverse event.

If a laboratory abnormality is one component of a diagnosis or syndrome, then only the diagnosis or syndrome should be recorded on the AE page/screen of the CRF. If the abnormality was not a part of a diagnosis or syndrome, then the laboratory abnormality should be recorded as the AE.

If possible, the laboratory abnormality should be recorded as a medical term and not simply as an abnormal laboratory result (eg, record thrombocytopenia rather than decreased platelets).

Adverse Laboratory values that also meet the definition of SERIOUS, will be reported as SAEs.

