6.3. Stopping Rule Triggers

Study drug dose should be paused per the guidelines in [Table 2](#) (using the Common Terminology Criteria for Adverse Events, Version 5.0 [CTCAE] for severity grading).

Table 2: Stopping Rule Triggers

If any of the following possibly related AEs occur:	At the first occurrence of any of the stopping rule triggers, discontinue Study Drug for the affected subject and pause further enrollment until DMC deliberations have been completed and a DMC decision that enrollment may be restarted has been rendered.

 • \geq Grade 3 (G3) non-hematologic toxicities • \geq G3 alanine aminotransferase (ALT) elevation OR \geq any ALT and total bilirubin elevation in combination which meet Hy's Law criteria [i.e., any \geq G3 hepatic impairment] • G3 thrombocytopenia with bleeding • G4 thrombocytopenia • G4 neutropenia • G3 neutropenia or thrombocytopenia in > 3 subjects • \geq G3 renal impairment including acute kidney injury requiring hemodialysis • Any SUSAR (suspected unexpected serious adverse reaction) 	

A DMC teleconference will be arranged within 5 business days of the stopping rule trigger. This should provide sufficient time for the CRO to prepare a blinded summary of the AE and the independent statistician to arrange to be unblinded to assist the DMC in its deliberations.

Additionally, the DMC will be provided with tabular safety summaries at 25%, 50% and 75% enrollment for ongoing surveillance.

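### Section 10.3 has no grade criterion for laboratory AEs, so the Table 2 count of Grade 3 cytopenias rests partly on investigator judgement (low severity, cheap to fix)

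*Protocol*

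**What the plan says.** Protocol section 6.3, Table 2, lists triggers that stop study drug for the affected subject and pause enrolment until the DMC has decided. Its lead-in confines them to AEs with a causality rating: "If any of the following possibly related AEs occur". Most triggers act on a single case: Grade 4 neutropenia, Grade 4 thrombocytopenia, Grade 3 thrombocytopenia with bleeding, any SUSAR, and events at or above "Grade 3 (G3) non-hematologic toxicities". One needs several subjects: "G3 neutropenia or thrombocytopenia in > 3 subjects". Once a trigger is met, "A DMC teleconference will be arranged within 5 business days of the stopping rule trigger". Separately, "the DMC will be provided with tabular safety summaries at 25%, 50% and 75% enrollment for ongoing surveillance".

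Whether a laboratory value is an AE is settled elsewhere. Section 10.1 admits laboratory values only under criteria given later, and section 10.3 supplies them. "An abnormal laboratory value is considered to be an AE if the abnormality" leads to study discontinuation; or needs treatment, a dose modification or interruption, or another intervention; or "is judged to be of significant clinical importance". If the abnormality belongs to a diagnosis or syndrome, "then only the diagnosis or syndrome should be recorded on the AE page/screen of the CRF". The only mention of CTCAE grade in section 10.3 concerns which abnormalities are documented as serious. Under section 10.2.3 the investigator rates relationship to study drug for each AE.

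**The concern.** Table 2 defines a count by CTCAE grade, but the entries that feed it pass through a rule that has no grade in it. A site can follow section 10.3 exactly, leave out an untreated Grade 3 neutropenia that it considers unimportant, and so keep that subject out of the count. The value then also gets no relationship rating, because only AEs are rated.

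At stake is the timing of one safety pause. The trigger needs four recorded subjects, so a single omitted entry can postpone it or prevent it when the true number is close to four. The scope is narrow, since the graver cytopenias and all the other triggers act on a single case.

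**Working it through.** **Step 1: how each cytopenia reaches Table 2 (protocol sections 6.3 and 10.3).**

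| Finding | Trigger alone? | What makes it an AE |
|---|---|---|
| Grade 4 neutropenia or thrombocytopenia | Yes, if possibly related | Table 2 stops the drug, which itself meets the dose-interruption condition |
| Grade 3 thrombocytopenia with bleeding | Yes, if possibly related | Same |
| Grade 3 neutropenia, or Grade 3 thrombocytopenia without bleeding | No, only through the count | Study discontinuation, treatment or dose change, otherwise judgement |

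In the third row Table 2 forces no drug stop, so it does not bring the value in through the dose-interruption condition. If the subject also stays on study and is untreated, judgement is the only route left.

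The syndrome rule is a minor second route. An unrelated diagnosis would not count in any case, and a possibly related non-haematological diagnosis of Grade 3 or higher triggers a pause by itself. That leaves related haematological or lower-grade diagnoses that absorb a Grade 3 cytopenia.

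**Step 2: what the plan quantifies.** It gives no operating characteristic for the count, so there is no figure to reproduce. The DMC tables fall at 0.25 × 80 = 20, 0.50 × 80 = 40 and 0.75 × 80 = 60 subjects.

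**Step 3: illustration near the threshold.** Assumptions, none from the documents: n subjects have a Grade 3 neutropenia or thrombocytopenia that would be rated possibly related; each is recorded as an AE with probability q, independently; no other safeguard intervenes. Then:

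- on time (the first four are all recorded) = q⁴
- count reached at all = P(Bin(n, q) ≥ 4)
- delayed = P(Bin(n, q) ≥ 4) − q⁴
- missed = 1 − P(Bin(n, q) ≥ 4)

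Worked case, n = 5 and q = 0.7: q⁴ = 0.240; count reached = 5 × 0.240 × 0.3 + 0.168 = 0.528; delayed = 0.288; missed = 0.472.

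| n | q | Reached | Delayed | Missed |
|---|---|---|---|---|
| 4 | 0.9 | 66% | 0% | 34% |
| 4 | 0.7 | 24% | 0% | 76% |
| 4 | 0.5 | 6% | 0% | 94% |
| 5 | 0.9 | 92% | 26% | 8% |
| 5 | 0.7 | 53% | 29% | 47% |
| 5 | 0.5 | 19% | 13% | 81% |
| 6 | 0.9 | 98% | 33% | 2% |
| 6 | 0.7 | 74% | 50% | 26% |
| 6 | 0.5 | 34% | 28% | 66% |

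A miss is more likely than a delay in 6 of the 9 rows. With exactly four qualifying subjects a delay is impossible, because any omission is a miss.

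**Step 4: illustration over full enrolment.** Take N = 80 with both arms pooled and a true rate r of qualifying subjects (assumed). The true count reaches four with probability P(Bin(80, r) ≥ 4), and the recorded count with P(Bin(80, rq) ≥ 4). Given a true count of four or more:

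| r | P(true count ≥ 4) | Delayed / missed, q = 0.9 | q = 0.75 | q = 0.5 |
|---|---|---|---|---|
| 2% | 7.7% | 8% / 26% | 11% / 58% | 5% / 89% |
| 5% | 57.2% | 20% / 15% | 30% / 38% | 18% / 75% |
| 10% | 96.5% | 32% / 3% | 57% / 11% | 53% / 41% |
| 20% | 100.0% | 34% / under 0.1% | 68% / 0.1% | 90% / 3.5% |

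The remainder in each cell is on time (q⁴ = 66%, 32% and 6%). With q = 1 the recorded count equals the true count, and under-recording causes neither delay nor miss.

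**The case against.** The strongest reply is that investigators are not left unguided. Section 10.2.2 describes Grade 3 as severe or medically significant, and Table 2 names Grade 3 neutropenia and thrombocytopenia outright, so a careful investigator has good reason to call such a value important. Haematology is drawn daily until discharge (Table 1). The monitor verifies source data and confirms that AEs are properly documented (section 11.1). The DMC sees safety tables three times and meets after any other trigger. Section 9.4.4 already lists laboratory abnormalities by toxicity grade. The DMC charter (section 4.1) and the Safety Management Plan (section 10.6) are not among the documents and may add surveillance. Leaving laboratory AEs to clinical judgement is a legitimate design choice.

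Most of this stands as mitigation and is why the point is minor. It does not close the gap, because none of these provisions requires an AE entry or a relationship rating. An omission that complies with section 10.3 gives a monitor no clear ground for a query. The contents of the DMC tables are not stated. The graded output in section 9.4.4 is not tied to the trigger, and SAP section 10.2 specifies only low/normal/high shifts.

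Three stronger readings are tempting and not supported:

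- A reader might infer that clinical judgement is always the only way in. Study discontinuation, treatment and dose change are separate routes.
- A reader might infer that a late pause is the usual result and a missed one the exception. Nothing in the documents orders the two. The illustrations go either way, and a miss dominates when events are few or recording is poor.
- A reader might take the low recording probabilities as a forecast. Nothing in the documents supports a value such as 0.5.

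**Conclusion.** The two rules do not match. Table 2 counts possibly related AEs at a stated CTCAE grade, while section 10.3 admits laboratory values as AEs without reference to grade. For a subject who stays on study, untreated and with dose unchanged, a Grade 3 neutropenia or non-bleeding thrombocytopenia counts only if the investigator judges it important. The pause for the cumulative trigger may therefore be delayed or missed.

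The size is unknown. The figures above rest on assumed event and recording rates, on independence between subjects, and on no safeguard intervening. They show only that the count is sensitive to one omission near four subjects, and that a miss becomes unlikely once qualifying subjects are well above four and recording is good.

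Severity is low: one trigger and one subset of events, with graver events covered singly. One limit applies. The protocol supplied is version 4.0, while the SAP says it is based on version 5.0, so section 10.3 should be checked in the later version.

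**What to change.** Add one sentence to section 10.3: any post-dose neutrophil or platelet value that newly reaches, or worsens from baseline to, a CTCAE grade named in Table 2 is recorded as an AE under its own term, with grade and relationship rating, whether or not it is treated, judged important or part of a syndrome.

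The baseline condition is needed. Section 5.2 sets no neutrophil or platelet limit, and section 10.1 defines an AE as something that appears or worsens, so an unchanged pre-existing low count should not be logged.

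Then check the running count of more than three subjects against the graded laboratory output already foreseen in section 9.4.4, produced during the trial with arms pooled so that the blind is kept, and query sites about missing entries. SAP section 10.2 should carry the same graded output. The Table 2 thresholds and the relatedness condition stay as they are.

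The cost is a few more AE entries and ratings, and prompt entry of local laboratory results. No new blood test is needed while subjects are in hospital. Relatedness remains an investigator's judgement, but one that is recorded and open to review.

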10.4. Pregnancy

All pregnancies or suspected pregnancies occurring in either a female subject of childbearing potential or partner of childbearing potential of a male subject are immediately reportable events.

10.4.1. Females of Childbearing Potential

Pregnancies and suspected pregnancies (including elevated β -hCG or positive pregnancy test in a female of childbearing potential regardless of disease state) occurring while the subject is on investigational product, or within 1 month after last dose of investigational product, are considered immediately reportable events. Investigational product is to be discontinued immediately. The pregnancy, suspected pregnancy, or positive pregnancy test must be reported Drug Safety immediately.

The female subject should be referred to an obstetrician-gynecologist, preferably one experienced in reproductive toxicity for further evaluation and counseling. The Investigator will follow the female subject until completion of the pregnancy and must notify Drug Safety immediately about the outcome of the pregnancy (either normal or abnormal outcome).

If the outcome of the pregnancy was abnormal (e.g., spontaneous abortion), the Investigator should report the abnormal outcome as an AE. If the abnormal outcome meets any of the serious criteria, it must be reported as an SAE to Drug Safety by facsimile, or other appropriate method, within 24 hours of the Investigator's knowledge of the event using the SAE Report Form or approved equivalent form.

All neonatal deaths that occur within 28 days of birth should be reported, without regard to causality, as SAEs. In addition, any infant death after 28 days that the Investigator suspects is related to the in-utero exposure to the investigational product should also be reported to Drug Safety within 24 hours of the Investigator's knowledge of the event.

10.4.2. Male Subjects

If a female partner of a male subject taking investigational product becomes pregnant at any time up to one month after the male subject's last dose of IP, the male subject taking investigational product should notify the Investigator, and the pregnant female partner should be advised to call their healthcare provider immediately.

10.5. Reporting of Serious Adverse Events

Any AE that meets any criterion for an SAE requires the completion of an SAE Report Form in addition to being recorded on the AE page/screen of the CRF. All SAEs must be reported to the Sponsor or the Sponsor's representative within 24 hours of the Investigator's knowledge of the event by facsimile, or other appropriate method, using the SAE Report Form, or approved equivalent form. This instruction pertains to initial SAE reports as well as any follow-up reports.

The Investigator is required to ensure that the data on these forms is accurate and consistent. This requirement applies to all SAEs (regardless of relationship to investigational product) that occur from the time the subject signs informed consent until the last study visit and those made known to the Investigator at anytime thereafter that are suspected of being related to investigational product. ALL SAEs occurring prior to treatment (after signing the ICF) will be captured.

The SAE report should provide a detailed description of the SAE and include a concise summary of hospital records and other relevant documents. If a subject died and an autopsy has been performed, copies of the autopsy report and death certificate are to be sent to the Sponsor or the Sponsor's representative as soon as these become available. Any follow-up data should be detailed in a subsequent SAE Report Form, or approved equivalent form, and sent to the Sponsor or the Sponsor's representative.

Where required by local legislation, the Investigator is responsible for informing the Institutional Review Board (IRB)/Ethics Committee (EC) of the SAE and providing them with all relevant initial and follow-up information about the event. The Investigator must keep copies of all SAE information on file including correspondence with the Sponsor or the Sponsor's representative and the IRB/EC.

10.6. Expedited Reporting of Adverse Events

For the purpose of regulatory reporting, the Sponsor will determine the expectedness of events suspected of being related to STI-5656 based on the [Investigator Brochure](#) and determine regulatory reporting according to local Health Authority requirements and according to the Safety Management Plan for the protocol.

Events of e.g. disease progression for the disease under study (including deaths due to disease progression for indications that are considered to be fatal) will be assessed but will not be usually

reported as expedited safety reports to regulatory authorities unless they otherwise meet the requirements for expedited reporting.

Where required by local legislation, the Investigator shall notify his/her IRB/EC promptly of new serious and unexpected AE(s) or significant risks to subjects communicated by the Sponsor.

The Investigator must keep copies of all pertinent safety information on file including correspondence with Drug Safety and the IRB/EC.

Sponsor or Sponsor's representative Contact Information for SAE reporting:

Please refer to the Serious Adverse Event Report Form.

11. DIRECT ACCESS TO SOURCE DATA/DOCUMENTS

11.1. Study Monitoring

Before an investigational site can enter a subject into the study, a representative of the Sponsor will pre-qualify the investigational study site to:

- Determine the adequacy of the facilities
- Discuss with the Investigator(s) and other personnel their responsibilities with regard to protocol adherence, and the responsibilities of the Sponsor or its representatives. This will be documented in a Clinical Study Agreement between the Sponsor and the Investigator.

As this study will be taking place during the COVID-19 pandemic, it is anticipated that most/all monitoring visits performed will be done remotely. This study will rely on the use of technology, either video or still camera pictures, to confirm facility requirements. The video or photo files will be stored in the Trial Master File.

During the study, a monitor from the Sponsor or its representative will have regular contacts with the investigational site, for the following:

- Provide information and support to the Investigator(s)
- Confirm that facilities remain acceptable
- Confirm that the investigational team is adhering to the protocol, that data are being accurately recorded in the case report forms, and that IP accountability checks are being performed
- Perform source data verification. This includes a comparison of the data in the case report forms with the subject's source records. This will require electronic access to all source records for each subject.
- Record and report any protocol deviations not previously sent to the Sponsor or its representative.
- Confirm AEs and SAEs have been properly documented on CRFs and confirm any SAEs have been forwarded to the Sponsor or its representative and those SAEs that met criteria for reporting have been forwarded to the IRB.

The monitor will be available between visits if the Investigator(s) or other staff needs information or advice.

